#### • Hyperthyroidism or Hypothyroidism:

Thyroid disorders can occur at any time during treatment. Monitor patients for changes in thyroid function (at the start of treatment, periodically during treatment, and as indicated based on clinical evaluation) and for clinical signs and symptoms of thyroid disorders.

- Grade 2 hyperthyroidism events (and Grade 3-4 hypothyroidism):
  - In hyperthyroidism, non-selective beta-blockers (e.g. propranolol) are suggested as initial therapy.
  - In hypothyroidism, thyroid hormone replacement therapy, with levothyroxine or liothyroinine, is indicated per standard of care.
- Grade 3-4 hyperthyroidism
  - Treat with an initial dose of IV corticosteroid followed by oral corticosteroids. When symptoms improve to Grade 1 or less, steroid

taper should be started and continued over no less than 4 weeks. Replacement of appropriate hormones may be required as the steroid dose is tapered.

- Hepatic:
  - For **Grade 2** events, monitor liver function tests more frequently until returned to baseline values (consider weekly).
    - Treat with IV or oral corticosteroids
  - For Grade 3-4 events, treat with intravenous corticosteroids for 24 to 48 hours.
  - When symptoms improve to Grade 1 or less, a steroid taper should be started and continued over no less than 4 weeks.

#### • Renal Failure or Nephritis:

- For Grade 2 events, treat with corticosteroids.
- For Grade 3-4 events, treat with systemic corticosteroids.
- When symptoms improve to Grade 1 or less, steroid taper should be started and continued over no less than 4 weeks.

**Management of Infusion Reactions**: Signs and symptoms usually develop during or shortly after drug infusion and generally resolve completely within 24 hours of completion of infusion.

Table 4 below shows treatment guidelines for subjects who experience an infusion reaction associated with administration of pembrolizumab (MK-3475).

	ease monitoring of vital signs as medically cated until the subject is deemed medically le in the opinion of the investigator.	None
not indicated; intervention not stabl indicated		
Requires infusion interruption but responds promptly to symptomatic treatment (e.g., antihistamines, NSAIDS, narcotics, IV fluids); prophylactic medications indicated for <=24 hrs	D Infusion and monitor symptoms. litional appropriate medical therapy may ude but is not limited to: IV fluids Antihistamines NSAIDS Acetaminophen Narcotics ease monitoring of vital signs as medically cated until the subject is deemed medically le in the opinion of the investigator. rmptoms resolve within one hour of stopping g infusion, the infusion may be restarted at to of the original infusion rate (e.g., from 100 hr to 50 mL/hr). Otherwise dosing will be until symptoms resolve and the subject ild be premedicated for the next scheduled c. jects who develop Grade 2 toxicity despite quate premedication should be manently discontinued from further trial tment administration.	Subject may be premedicated 1.5h (± 30 minutes) prior to infusion of pembrolizumab (MK-3475) with: Diphenhydramine 50 mg po (or equivalent dose of antihistamine). Acetaminophen 500-1000 mg po (or equivalent dose of antipyretic).

 Table 4 Infusion Reaction Treatment Guidelines

NCI CTCAE Grade	Treatment	Premedication at subsequent dosing
Grades 3 or 4	Stop Infusion.	No subsequent dosing
Grade 3: Prolonged (i.e., not rapidly responsive to symptomatic medication and/or brief interruption of infusion); recurrence of symptoms following initial improvement; hospitalization indicated for other clinical sequelae (e.g., renal impairment, pulmonary infiltrates)	Additional appropriate medical therapy may include but is not limited to: IV fluids Antihistamines NSAIDS Acetaminophen Narcotics Oxygen Pressors Corticosteroids Epinephrine	
Grade 4: Life-threatening; pressor or ventilatory support indicated	Increase monitoring of vital signs as medically indicated until the subject is deemed medically stable in the opinion of the investigator. Hospitalization may be indicated. Subject is permanently discontinued from further trial treatment administration.	

#### 5.7.2 Supportive Care Guidelines for Cisplatin

Based on local standard practices the chemotherapy regimen is considered moderate emesis potential. Prevention and/or treatment of nausea and vomiting should be managed with the following regimen initially:

Prior to each cisplatin dose:

- 1. Fosaprepitant 150 mg IV day 1 or aprepitant 3 day pack (125 mg day 1, 80 mg days 2 and 3)
- 2. Palonosetron 0.25 mg IV day 1

Additional scheduled antiemetic support can include (per investigator discretion):

- 1. Ondansetron 8 mg two times a day starting 1 day following palonsetron
- 2. Prochlorperazine 10 mg IV/PO 3-4 times per day
- 3. Olanzapine 5-10mg PO days 1-4
- 4. Granisetron transdermal patch 3.1mg/day; maximum duration of patch is 7 days
- 5. Lorazepam 0.5-2mg PO/IV every 4-6 hours
- 6. H2 blocker or proton pump inhibitor

Additional as needed antiemetics can be used per local standards. However, due to the immunologic nature of this trial, corticosteroids, including dexamethasone should not be used unless Grade 4 nausea occurs. If this occurs, dexamethasone 4 mg IV/PO can be used as a premedication for cisplatin. If Grade 4 nausea still occurs, despite dexamethasone 4 mg IV/PO, additional corticosteroid can be used after discussion with the principal investigator.

Please refer to the product label or local standards of care for additional cisplatin supportive measures.

Hydration and electrolyte replacement may be utilized per the discretion of the treating physician provided adequate pre/post cisplatin hydration is achieved and renal function remains adequate.

#### 5.7.3 Supportive Care Guidelines for Radiation

Please refer to local standards of care for additional supportive measures for radiation.

#### 5.8 **Diet/Activity/Other Considerations**

#### 5.8.1 **Diet**

Subjects should maintain a normal diet unless modifications are required to manage an AE such as diarrhea, nausea or vomiting.

#### 5.8.2 Contraception

Pembrolizumab may have adverse effects on a fetus in utero. Furthermore, it is not known if pembrolizumab has transient adverse effects on the composition of sperm. Non-pregnant, non-breast-feeding women may be enrolled if they are willing to use 2 methods of birth control or are considered highly unlikely to conceive. Highly unlikely to conceive is defined as 1) surgically sterilized, or 2) postmenopausal (a woman who is  $\geq$ 45 years of age and has not had menses for greater than 1 year will be considered postmenopausal), or 3) not heterosexually active for the duration of the study. The two birth control methods can be either: two barrier methods or a barrier method plus a hormonal method to prevent pregnancy. Subjects should start using birth control from study Visit 1 throughout the study period up to 120 days after the last dose of study therapy.

The following are considered adequate barrier methods of contraception: diaphragm, condom (by the partner), vasectomy, copper intrauterine device, sponge, or spermicide. Appropriate hormonal contraceptives will include any registered and marketed contraceptive agent that contains an estrogen and/or a progestational agent (including oral, subcutaneous, intrauterine, or intramuscular agents).

Subjects should be informed that taking the study medication may involve unknown risks to the fetus (unborn baby) if pregnancy were to occur during the study. In order to participate in the study they must adhere to the contraception requirement (described above) for the duration of the study and during the follow-up period defined in section 7.2.2-Reporting of Pregnancy and Lactation to Sanford Research and to Merck. If there is any question that a subject will not reliably comply with the requirements for contraception, that subject should not be entered into the study.

#### 5.8.3 Use in Pregnancy

If a subject inadvertently becomes pregnant while on treatment with pembrolizumab, the subject will immediately be removed from the treatment phase of the study. The site will contact the subject at least monthly and document the subject's status until the pregnancy has

been completed or terminated. The outcome of the pregnancy will be reported to Sanford Research and to Merck without delay and within 24 hours to Sanford Research and within 2 working days to Merck if the outcome is a serious adverse experience (e.g., death, abortion, congenital anomaly, or other disabling or life-threatening complication to the mother or newborn).

The study investigator will make every effort to obtain permission to follow the outcome of the pregnancy and report the condition of the fetus or newborn to Sanford Research. If a male subject impregnates his female partner the study personnel at the site must be informed immediately and the pregnancy reported to Sanford Research and to Merck and followed as described above and in Section 7.2.2.

#### 5.8.4 Use in Nursing Women

It is unknown whether pembrolizumab is excreted in human milk. Since many drugs are excreted in human milk, and because of the potential for serious adverse reactions in the nursing infant, subjects who are breast-feeding are not eligible for enrollment.

#### 5.8.4.1 **Pembrolizumab**

It is unknown whether pembrolizumab is excreted in human milk.

#### 5.8.4.2 Cisplatin

Cisplatin has been reported to be found in human milk; subjects receiving Cisplatin injection should not breast-feed.

#### 5.9 Subject Withdrawal/Discontinuation Criteria

Subjects may withdraw consent at any time for any reason or be withdrawn from the trial at the discretion of the investigator should any untoward effect occur. In addition, a subject may be withdrawn by the investigator or principal investigator if enrollment into the trial is inappropriate, the trial plan is violated, or for administrative and/or other safety reasons. Specific details regarding discontinuation or withdrawal are provided in Section 7.1.4 – Other Procedures.

A subject must be discontinued from the trial for any of the following reasons:

- The subject or legal representative (such as a parent or legal guardian) withdraws consent.
- Confirmed radiographic disease progression
- Unacceptable adverse experiences as described in Section 5.2.1.2
- Intercurrent illness that prevents further administration of treatment

- Investigator's decision to withdraw the subject
- The subject has a confirmed positive serum pregnancy test
- Noncompliance with trial treatment or procedure requirements
- The subject is lost to follow-up
- Administrative reasons

The End of Treatment and Follow-up visit procedures are listed in Section 6 (Protocol Flow Chart) and Section 7.1.5 (Visit Requirements). For those subjects discontinue treatment early, each subject will be followed for 30 days for adverse event monitoring (serious adverse events will be collected for 90 days after the end of treatment as described in Section 7.2.3.1). Subjects who discontinue for reasons other than progressive disease will have post-treatment follow-up for disease status until disease progression, initiating a non-study cancer treatment, withdrawing consent or becoming lost to follow-up. After documented disease progression each subject will be followed for overall survival until death, withdrawal of consent, or the end of the study, whichever occurs first.

#### 5.10 Subject Replacement Strategy

A subject who discontinues from the trial during the active treatment for reasons other than AE/SAE or progression will be replaced.

#### 5.11 Clinical Criteria for Early Trial Termination

Early trial termination will be the result of the criteria specified below:

- 1. Quality or quantity of data recording is inaccurate or incomplete
- 2. Poor adherence to protocol and regulatory requirements
- 3. Incidence or severity of adverse drug reaction in this or other studies indicates a potential health hazard to subjects

### 6.0 TRIAL FLOW CHART

## 6.1 Screening and Concurrent Treatment Phase

	Screening Visit				Treatm	ent Days 				
Treatment Day	-36 to -8	-7	1	8	15	22	29	36	43	50
Scheduling Window  (days)		+4	+/-2	+/-2	+/-2	+/-2	+/-2	+/-2	+/-2	+/-2
Administrative Procedures										
Informed consent	X									
Informed consent correlative research	x									
Inclusion/exclusion criteria	X									
Demographics and medical history	X									
Prior and concomitant medications	X	X	X	X	X	X	X	X	X	X
Disease specific details	X									
Clinical Procedures and Assessme	nts									
Adverse Events		x	X	X	x	X	x	X	X	X
Full Physical Exam	X									
Directed Physical Exam		X	x	x	x	x	x	x	x	

	Screening Visit				Treatm	ent Days 				
Treatment Day	-36 to -8	-7	1	8	15	22	29	36	43	50
Scheduling Window  (days)		+4	+/-2	+/-2	+/-2	+/-2	+/-2	+/-2	+/-2	+/-2
Vitals and Weight 	X	X	X	X	X	X	x	x	x	
ECOG PS	X	X	X	x	x	x	x	x	X	
Study Treatments										
Pembrolizumab		X			X			X		
Cisplatin			X	X	X	X	x	x		
Radiation 			X	X	X	X	x	x	x	X
Laboratory Procedures/Assessme	ents (local laboratory	y testing):					[	 		
Pregnancy Test 	X									
CBC with differential	X	x 	X	X	X	X	x	x	x	X
Serum Chemistry Panel 	X	x 	X	X	X	X	x	x	x	X
Uric Acid	X	x 	X	x	x	x	x	x	X	x
Magnesium, Phosphorus, LDH	X	x 	X	X	X	X	X	X	x	x
T3, FT4, TSH	x				X			X		

	Screening Visit				Treatm	ent Days 				
Treatment Day	-36 to -8	-7	1	8	15	22	29	36	43	50
Scheduling Window  (days)		+4	+/-2	+/-2	+/-2	+/-2	+/-2	+/-2	+/-2	+/-2
Urinalysis	X				x			x		
P16 testing 	X									
Imaging				 		 		 	I	
Tumor Imaging (CT neck  , PET  )	x									
Correlative Study Procedures			 				 	 		
Tumor tissue collection 	X									
Blood for correlative studies 		X			x			x		
Patient Reported Outcomes (PRO	))		1	l	1	l	1	1	I	
FACT H&N 		X						X		

# 6.2 Adjuvant Treatment Phase

		Treatment Days 							
Treatment Day	57	78	99	120	141	150			
Scheduling Window (days) 	-3/+7	-3/+7	-3/+7	-3/+7	-3/+7	-7/+14			
Administrative Procedures						_			
Prior and concomitant medications	x	x	x	x	x	X			
Clinical Procedures and Assessments									
Adverse Events	x	x	x	x	x	x			
Directed Physical Exam	X	X	x	X	X	x			
Vitals and Weight	X	x	x	X	X	x			
ECOG PS	X	X	x	X	X	X			
Study Treatments						1			
Pembrolizumab 	X	X	x	X	X				

		Tre	atment Days 			Treatment End	
Treatment Day	57	78	99	120	141	150	
Scheduling Window (days) 	-3/+7	-3/+7	-3/+7	-3/+7	-3/+7	-7/+14	
Laboratory Procedures/Assessments (local la	boratory testing):						
CBC with differential	x	x	x	x	x	x	
Serum Chemistry Panel 	x	X	X	x	x	x	
Uric Acid	x	x	x	x	x	x	
Magnesium	x						
Urinalysis	x	x	x	x	x	x	
T3, FT4, TSH				x		x	
Imaging					 		
Tumor Imaging (CT neck  , PET  )						x	
Correlative Study Procedures							
Blood for correlative studies 		X		x		x	
Salvage surgery collection 						x	
Patient Reported Outcomes (PRO)					I		
FACT H&N 		x				x	

# 6.3 Follow-up

		Months Following Study Treatment End (after day 150 imaging)								
Follow-up Month	Follow up visit 1 (90 days from Day 150)	Follow up visit 2 (90 days from FU-V1)	Follow up visit 3 (180 days from FU-V2)	Follow up visit 4 (180 days from FU-V3)	Follow up visit 5 (180 days from FU-V4)	Follow up visit 6 (352 days from FU-V5)	Follow up visit 7 (352 days from FU-V6)	Follow up visit 8 (352 days from FU-V7)	Study End	
Scheduling Window	+/- 14 days	+/- 30 days	+/- 30 days	+/- 30 days	+/- 30 days	+/- 30 days	+/- 30 days	+/- 30 days		
Administrative Procedures									]	
Subsequent antineoplastic therapy status	x	X	X	X	X	x	X	X		
Survival Status 	X	x	x	x	x	x	x	X	-	
Clinical Procedures and Asses	sments				I		I		1	
Adverse Events 	x	X	X	X	x	x	x	x	-	
Directed Physical Exam	x	x	X	X	x	X	x	x		
Vitals and Weight (optional)	x	x	X	X	x	X	x	x		
ECOG PS(optional)	X	x	x	X	X	X	X	X		

	Months Following Study Treatment End (after day 150 imaging)								
Follow-up Month	Follow up visit 1 (90 days from Day 150)	Follow up visit 2 (90 days from FU-V1)	Follow up visit 3 (180 days from FU-V2)	Follow up visit 4 (180 days from FU-V3)	Follow up visit 5 (180 days from FU-V4)	Follow up visit 6 (352 days from FU-V5)	Follow up visit 7 (352 days from FU-V6)	Follow up visit 8 (352 days from FU-V7)	Study End
Scheduling Window	+/- 14 days	+/- 30 days	+/- 30 days	+/- 30 days	+/- 30 days	+/- 30 days	+/- 30 days	+/- 30 days	
Laboratory Procedures/Assess	nents (local labor	atory testing):							
CBC with differential	x	x	x	x	x	X	x	x	-
Serum Chemistry Panel 	X	x	x	X	x	X	x	x	-
T3, FT4, TSH		x	X	X	X	X	x	x	
Imaging									-
Tumor Imaging (CT neck)	X	x	x		x	x	x	x	-
Correlative Study Procedures	 	I	 						
Blood for correlative studies 			x						
Patient Reported Outcomes (PI	RO)				 			 	
FACT H&N 			x		x				

1. Treatment day 1 coincides with the first day of radiation therapy. Any treatment days before will be denoted with a preceding (-) symbol.

2. The window for each visit is outlined as above. If a treatment is delayed, the following treatment must occur with the same delay. Additional treatment delay can occur with the specified scheduling window. If treatment is delayed beyond that window, treatment for that scheduled course must be held. Treatment can be resumed for the next scheduled treatment day.

3. Radiation occurs continuously throughout therapy until the total of 35 fractions has been completed. Therefore, the dates listed may not always have radiation treatment on that date. All radiation should be completed by day 52.

4. For women of reproductive potential, a urine pregnancy test will be performed within 72 hours prior to the first dose of trial treatment. If urine pregnancy tests cannot be confirmed as negative, a serum pregnancy test, performed by the local lab, will be required. Pregnancy tests (serum and/or urine tests) should be repeated if required by local guidelines.

5. The serum chemistry panel includes tests listed in Section 7.1.3, Table 5(Albumin, AST, ALT, Alkaline phosphatase, Total Bilirubin (and direct bilirubin if elevated), Total Protein, CO2, Calcium, Chloride, Glucose, Potassium, Sodium, Creatinine, and BUN).

6. p16 immunohistochemistry status is required on all patients. This can be performed by the local laboratory sites. High risk HPV DNA testing at an outside lab can be performed if p16 staining is indeterminate or not able to be obtained. See section 5.1.2 for details.

7. Tumor tissue for biomarker analysis from an archival tissue sample or fresh biopsy must be provided for enrollment. Detailed instructions for tissue collection, processing and shipment are included in the procedures manual.

10. Blood for correlative flow cytometry studies will be drawn throughout treatment. On days with corresponding treatment, this should be drawn within 24 hours prior to treatment with pembrolizumab or chemotherapy. Procedures for sample collection, processing, and shipment are included in the procedures manual.

11. Patient reported outcomes (PRO) will be assessed using the FACT H&N form (see Appendix 11.8). PRO forms must be completed on paper or electronically by subjects prior to all other study procedures for that date. Patients who go off-treatment but continue follow up should be encouraged to complete PRO at the times outlined in the calendar.

12. Tumor imaging will be completed at baseline and after treatment has finished, on approximately day 150-157. Baseline imaging must be completed within 42 days of enrollment. Required imaging for the study protocol is diagnostic quality imaging of the neck. Additional imaging techniques can be utilized (i.e. MRI, FDG-PET, etc.), but are not required for study procedures.

13. Patients with residual disease (SD, PR, or PD) on post-treatment imaging will undergo salvage surgical resection (at the discretion of the surgeon) if their disease is felt curable with salvage surgery. Additionally, patients with a CR and clinical suspicion for viable residual disease will be offered salvage surgery. Following pathology analysis, salvage surgical tissue will be sent for correlative studies. Detailed instructions for tissue collection, processing, and shipment are included in the procedures manual.

14. PET imaging at baseline and treatment end is not required for the study, but is allowed for use to determine complete response rate when tumor response on standard imaging cannot confirm CR based on RECIST 1.1. Please see sections 7.1.2.6.2 and 7.1.2.6.3 for details.

15. Screening labs completed within 7 days (168 hours) of treatment initiation (day -7) will not need to be repeated.

16. Once a subject experiences confirmed disease progression or starts a new anti-cancer therapy, the subject moves into the Survival Follow-Up Phase. These subjects will be followed every 6 months to assess for survival status until death, withdrawal of consent, or the end of the study, whichever occurs first.

17. If a subject discontinues pembrolizumab, return visit timing is left to treating physician discretion until day 150 although it is highly recommended that the subject return for Day 78, 120, and 150 so research specimens and QOL can be collected.

18. Minimum interval between pembrolizumab doses is 14 days.

19. Vital signs and weight do not need to occur on the same day as the visit but need to be completed within the window and prior to the next treatment.

20. Once a subject transitions to follow-up all documented AEs will be followed until resolution or to a new baseline as determined by the treating investigator. Only new AEs that could be considered an ECI or irAR will be documented and followed while in follow-up.

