#### 3.2 Secondary Objective(s) & Hypothesis (es)

1. **Objective:** To estimate progression-free survival (PFS), overall survival (OS), the locoregional control rate (LRC), and distant metastases (DM) rate at 1- and 2-years in subjects treated with pembrolizumab given in combination with CRT.

**Hypothesis**: The addition of pembrolizumab to standard CRT will show increased efficacy in terms of key survival endpoints utilized in head and neck cancer.

2. **Objective:** To determine the best overall response rate (ORR) as defined by RECIST 1.1 at treatment end imaging in subjects with Stage III-IVB SCCHN treated with pembrolizumab given in combination with CRT.

**Hypothesis**: The addition of pembrolizumab to standard CRT will show superior ORR compared to historical controls.

4. **Objective:** To estimate the quality of life (QOL) of subjects with Stage III-IVB SCCHN treated with pembrolizumab in combination with CRT during therapy, treatment end, and 1- and 2-years following treatment.

**Hypothesis**: Acute and long-term QOL of participants treated with the combination of pembrolizumab and low dose weekly cisplatin and radiation will be superior to historical controls.

5. **Objective:** To correlate ORR, PFS, OS, LRC, and DM with tumor PD-L1 expression in subjects with Stage III-IVB SCCHN treated with pembrolizumab in combination with CRT.

**Hypothesis**: High PD-L1 expression has correlated with responses in the metastatic setting and will correlate with key disease response and survival outcomes in the curative intent setting.

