A final supportive outcome of importance is patient-related outcomes (PRO). High-dose bolus cisplatin is highly toxic and leads to severe acute and late effects for patients. Survivors of head and neck cancer experience some of the most severe late effects from therapy [32]. During treatment, the majority of patients will require feeding tubes as they will develop severe mucositis, dysphagia/odynophagia, nausea/vomiting, loss of appetite, xerostomia/sialorrhea, and malnutrition [12]. Fatigue, difficulties with speech, and inability to eat can affect mood. It may take anywhere from 12-36 months for most patients to return back to an acceptable baseline quality of life (QOL) [33]. Some patients will never return to a self-rated acceptable QOL. The factors degrading QOL are complex, but include psychosocial symptoms and chronic somatic changes related to the disease and associated treatment [34]. Many feel that low-dose weekly cisplatin may be better tolerated and have improved QOL indices [17]. We feel that QOL is an extremely important endpoint to evaluate when developing a novel combination as proposed. This is important, as even if efficacy is improved, if QOL is significantly degraded, it may not be worthwhile to move forward with further testing. Fortunately, we have QOL data, using the Functional Assessment of Cancer Therapy Head and Neck (FACT H&N) survey, from approximately 50 patients treated with standard of care, highdose bolus cisplatin in this setting for comparison at approximate time points as outlined in this study [35]. We propose using the same OOL survey for this study. While it is not a head to head comparison in a randomized trial, it does provide insight into how this combination may be tolerated in a phase III comparison to standard therapy.

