#### 7.1.2.6.2 Tumor Imaging During Trial

The first imaging assessment should be performed at approximately **100 days after completion of radiation therapy**. For the purposes of this study, this is considered the "treatment end" imaging study. This will be approximately day 150 from the first dose of radiation. Due to treatment variations and delays, this may be delayed by up to 14 days.

Follow-up imaging will occur at scheduled intervals outlined on the Flow Chart. At 1 year following completion of the study treatment PET/CT imaging is not required, but is suggested

and is allowed so long as diagnostic quality CT images are included. Diagnostic quality imaging of the primary tumor site (CT scan of the neck) should be performed annually thereafter for up to 5 years. Images will be reviewed by the central radiologist at the end of the study to confirm disease response for purposes of study evaluation.

Additional imaging should be performed per clinical guidelines and is not required the study. Patients with clinical signs and symptoms of progression should have follow-up imaging as deemed clinically necessary. If this occurs during the study period, it should be reported to the study.

During the follow up period, if an instance occurs where the participants insurance will not approve a diagnostic CT scan a clinical evaluation will be used. No protocol deviation is needed but the insurance denial must be documented on the tumor assessment source documents.

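### Each follow-up visit is timed from the visit before it, so the 1- and 2-year quality-of-life assessments can drift by up to 74 and 134 days within the rules

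*Combined protocol and SAP*

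**What the plan says.** The follow-up table in section 6.3 counts time from treatment end, after the Day 150 imaging. Only the first visit is tied to that point: "Follow up visit 1 (90 days from Day 150", with a window of 14 days either way. From there the visits form a chain. The second is given as "Follow up visit 2 (90 days from FU-V1". The third and fourth are likewise each set 180 days after their predecessor, the visit that serves as two years is listed as "Follow up visit 5 (180 days from FU-V4", and the same pattern runs on to the eighth. Each visit from FU-V2 onward has a window of 30 days either way. The Day 150 visit has its own window of -7/+14 days (section 6.2).

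The quality-of-life objective in section 3.2 sets its time points as "during therapy, treatment end, and 1- and 2-years following treatment". In the flow chart, FU-V3 and FU-V5 are the only follow-up visits with FACT H&N. Section 8.4.6 also lists a six-month questionnaire and gives the one-year point twice, but section 6.3 schedules no FACT H&N between treatment end and FU-V3. Both FU-V3 and FU-V5 also carry a neck CT.

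**The concern.** The objective names fixed times after treatment, but the schedule does not hold visits to fixed times. A site that follows the table literally must re-base each visit on the last one, so a late visit moves every later one back and an early visit moves them all forward.

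This matters most for quality of life. Section 4.2.3.2 says: "It may take anywhere from 12-36 months for most patients to return back to an acceptable baseline quality of life (QOL". Both FACT H&N follow-up visits therefore fall where scores may still be changing, and the flow chart provides no neighbouring score to replace one taken far off target. Sections 8.4.3.2 and 8.4.6 compare these scores over time with historical controls, and section 4.2.3.2 relies on the two series having roughly matching time points. Scatter in timing blurs that match. A systematic shift to later visits would give trial patients extra recovery time.

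**Working it through.** The plan gives no figure for cumulative drift, so there is none to reproduce. All inputs are the intervals and windows in sections 6.2 and 6.3.

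**1. Limits, measured from the actual treatment-end visit.** Chained limit = sum of the windows from FU-V1 to the visit in question.

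| Visit | Nominal days after treatment end | Chained limit | Limit if anchored |
|---|---|---|---|
| FU-V1 | 90 | ±14 | ±14 |
| FU-V2 | 90 + 90 = 180 | 14 + 30 = ±44 | ±30 |
| FU-V3 | 180 + 180 = 360 | 14 + 2×30 = ±74 | ±30 |
| FU-V4 | 360 + 180 = 540 | 14 + 3×30 = ±104 | ±30 |
| FU-V5 | 540 + 180 = 720 | 14 + 4×30 = ±134 | ±30 |

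FU-V3 can therefore fall 286 to 434 days after treatment end, and FU-V5 586 to 854 days after. Against calendar years (365 and 730 days) the limits are -79/+69 and -144/+124 days.

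**2. Typical spread.** The documents do not say how sites use the windows. Assume independent errors, uniform over each window. A uniform error over a range of width w has variance w²/12, so:

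- FU-V3 chained: SD = √[(28² + 2×60²)/12] = 25.8 days
- FU-V5 chained: SD = √[(28² + 4×60²)/12] = 35.6 days
- Either visit anchored: SD = √(60²/12) = 17.3 days

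Simulation under the same assumption puts about 27% of FU-V3 and 41% of FU-V5 visits more than 30 days off target. Anchored, the share is zero by construction.

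**3. 1-year PFS.** PFS runs from Day -7 (section 8.4.1), so one year is about day 358. The last scheduled scan before it is FU-V2, nominally on day 150 + 180 = 330. Under uniform use, the share of FU-V2 scans after day 358 is:

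- chained: 12.4%
- anchored to the actual treatment-end visit: 10.1%
- anchored to the nominal Day 150 date: 3.3%

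So most of the slippage past day 358 comes from the Day 150 window, not from chaining. If 5-10% of patients progressed silently between FU-V1 and FU-V2 (an assumption without a source in the plan), anchoring to the actual visit would change 1-year PFS by (12.4% - 10.1%) × 5-10%, which is about 0.1 to 0.2 percentage points. For comparison, the 95% half-width for a proportion of 70-85% in 57 patients is 1.96 × √[p(1 - p)/57], or about 12 to 9 points.

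**4. Cost of anchoring to scan gaps.** FU-V2 to FU-V3 is now 180 ± 30 = 150-210 days and would become 180 ± 60 = 120-240. FU-V5 to FU-V6 is now 352 ± 30 = 322-382 days and would become 292-412.

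**The case against.** **The limits are corner cases.** They need every window used fully in the same direction. This stands. Even with the Day 150 window added, uniform use puts only 9.9% of FU-V5 visits more than 60 days off and 0.3% more than 100 days off. The case rests on the typical spread, not on the extremes.

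**A reader might infer larger drifts**, of -81/+88 days at FU-V3 and -141/+148 days at FU-V5. Those sums are correct against study days 510 and 870, but they include the Day 150 window. The table and the quality-of-life objective both count from treatment end, so that window is not drift on the protocol's own clock.

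**A reader might infer that 1-year PFS is materially overstated.** The documents do not support this. Chaining adds little once the Day 150 window is set aside. A large effect needs both an unsourced rate of silent progression and every patient attending in the late half of every window. PFS is also a secondary, unpowered endpoint, and section 7.1.2.6.2 provides for extra imaging when there are signs or symptoms.

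**The analysis may absorb the drift.** A linear mixed model can use actual assessment dates, recovery over 12-36 months is slow relative to an SD of 36 days, and the historical comparison is only approximate anyway. This partly stands, and the harm in FACT H&N points cannot be quantified from the documents. But the plan does not say that actual dates will be used, and modelling does not restore a score at the intended time.

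**The imaging text does not conflict with the chain.** Section 7.1.2.6.2 mentions one year ("At 1 year following completion of the study treatment PET/CT imaging is not required") but defers to the flow chart for scan intervals. This stands, so the conflict is with the quality-of-life objective only.

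**The sponsor may have meant a nominal calendar.** That is possible, but the text does not say so.

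**Conclusion.** The point holds as a scheduling weakness that is cheap to remove. Visits fully within the rules can miss the 1-year point by up to 74 days and the 2-year point by up to 134 days from actual treatment end. Under uniform window use, about 27% and 41% miss by more than 30 days, with SDs of about 26 and 36 days against 17 if anchored. The limits follow from the flow chart alone. The percentages and SDs rest on the assumption of independent, uniform use of the windows.

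The consequence is mainly less well-defined 1- and 2-year FACT H&N results and a looser comparison with historical controls. Any effect on 1-year PFS is small. OS uses the actual date of death and is unaffected, and the primary complete-response endpoint is assessed before this schedule begins.

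**What to change.** In section 6.3, state every follow-up visit as fixed days from the actual treatment-end (Day 150) visit: 90, 180, 360, 540 and 720 days, then the later visits at their existing cumulative intervals (1072, 1424 and 1776 days). Keep the present windows. A late or early visit then no longer moves the ones after it.

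The actual visit is a better anchor than the nominal Day 150 date, because the quality-of-life objective counts from the end of treatment. Anchoring to the nominal date would bring visits too early for patients whose treatment ended late.

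The change is to flow-chart wording, with no added visits or procedures. Its price is more variable spacing: the next gap is shorter after a late visit and longer after an early one, for example 120-240 days between FU-V2 and FU-V3 instead of 150-210. Visits already made cannot be re-timed, so their actual time since treatment end should be reported with the FACT H&N results.
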